8.2.2. Visit 2: First study drug course

(As soon as the biologic results of screening are available, no later than 4 weeks after the start of the screening).

The following study procedures will be carried out at the 1st study drug course:

- Before the 1st study drug course (within 24 hours before study drug course)
 - Complete physical examination.
 - Biometric information: weight.
 - Vital signs: temperature, heart rate, systolic and diastolic blood pressure.
 - Baseline neurological status assessment:
 - INCAT disability score (adjusted INCAT disability score will be deduced from reported values).
 - Patient and Investigator CGI-S.
 - MRC-sum-score.
 - Rasch-modified MRC sum score.
 - R-ODS.
 - Grip strength with Martin vigorimeter in both hands.
 - Biological tests in local laboratory:
 - Serum total IgG trough levels.
 - C3 and C4 antigens.
 - Serum reference sample for long term storage.
 - Analysis at centralised laboratory:
 - BAFF.
 - CH50.
 - FcγRIIB.

- AEs assessment.
- Listing of concomitant medication.
- Patient diary verification. If information on the patient's diary is not clear, the Investigator will ask the patient questions. The investigator may annotate the patient's diary but must date and sign the annotations.
- During the course of study drug infusion:
 - Collection of infusion parameters.
 - Vital signs measured 30-45 min and 60-75 min after the beginning of the infusion: temperature, heart rate, systolic and diastolic blood pressure.
 - Listing of concomitant medication if applicable.
 - AEs assessment.
- 30-45 min after the end of study drug infusion:
 - Vital signs: temperature, heart rate, systolic and diastolic blood pressure.
 - AEs assessment.
 - Listing of concomitant medication if applicable.

8.2.3. Visit 3: 96 hours after the end of the first course (+/- 24 hours)

The following study procedures will be carried out:

- Complete physical examination.
- Vital signs: temperature, heart rate, systolic and diastolic blood pressure.
- Biological tests in local laboratory:
 - Haematology:
 - Complete blood count + differentials, Hb, MCV, platelets count.
 - Haptoglobin.
 - Biochemical:
 - Creatininemia, glomerular filtration rate according to MDRD.
 - LDH.
 - Total and free bilirubin (total and free bilirubin (total bilirubin in all patients; if total bilirubin > ULN, free bilirubin will be assessed from the same blood sample, as total bilirubin).
 - C3 and C4 antigens.

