2.6. Study Plan Table

	Screening	First study drug administration	Day 4 after last infusion at V2	Week 3	Week 6	Week 9	Week 12	Week 15	Week 18	Week 21	End of study visit
	VISIT 1	VISIT 2	VISIT 3	VISIT 4	VISIT 5	VISIT 6	VISIT 7	VISIT 8	VISIT 9	VISIT 10	VISIT 11
Informed consent (before any procedure of study)	X										
Inclusion/exclusion criteria verification	X	X									
Demographics & Medical history	X										
Safety											
Adverse events assessment	X	X	X	X	X	X	X	X	X	X	X
Phone call 4 days (+/- 1 day) after study drug administration				X	X	X	X	X	X	X	
Concomitant medications	X	X	X	X	X	X	X	X	X	X	X
Patient diary (delivery and verification)	X	X	X	X	X	X	X	X	X	X	X
Clinical assessments / Before study drug administration											
Complete physical examination	X	X	X								X
Clinical examination focused on arterial or venous thromboembolic signs				X	X	X	X	X	X	X	
Weight, Body temperature, heart rate, arterial blood pressure (systolic and diastolic)	X	X	X	X	X	X	X	X	X	X	X
Efficacy assessments / Before study drug administration											
INCAT disability score	X	X		X	X	X	X	X	X	X	X
MRC sum-score, Rash modified MRC sum-score R-ODS Grip Strength (both hands)		X					X				X
Patient and Investigator: CGI (Severity)		X					X				X
Patient and Investigator: CGI (Efficacy), CGI (Improvement)							X				X

Biological test Local lab / Before study drug administration	VISIT 1	VISIT 2	VISIT 3	VISIT 4	VISIT 5	VISIT 6	VISIT 7	VISIT 8	VISIT 9	VISIT 10	VISIT 11
Serum Total IgG trough levels		X		X	X	X	X	X	X	X	X
HbA1c (only for patients with a known history of diabetes mellitus), serum IgA levels	X										
Urine protein reagent strip test	X ^a		X ^b	X ^b	X ^b	X ^b	X ^b	X ^b	X ^b	X ^b	X ^b
Urine Pregnancy test for female of child bearing potential	X										X
C3 and C4 antigens		X	X	X							X
Anti HBs & anti HBc Ab, HBs Ag tests, HIV and HCV tests	X										X
Complete blood count and differentials, Hemoglobin, Mean corpuscular volume, platelet count, haptoglobin, LDH	X		X	X	X	X	X	X	X	X	X
Reticulocytes, direct Coombs test, total serum protein level	X										X
AST, ALT, γ GT, ALP	X										X
Creatininemia, GFR ^c , total and free bilirubin ^d	X		X	X	X	X	X	X	X	X	X
Serum reference sample for long term storage		X									X
Biological test Local lab in case of suspected clinical thrombosis											
D-Dimers		X	X	X	X	X	X	X	X	X	X
Biological test Local lab in case of suspected hemolysis											
Reticulocytes, direct Coombs test		X	X	X	X	X	X	X	X	X	X

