3.4. Multiplicity Issues, Subgroup Analysis, Interim Analysis, Blinding and Randomisation

All analyses will be presented according to the following subgroups and overall:

- Ig-naïve patients
- Relapsing Ig-pretreated patients

However, statistical tests will be performed only for the overall population (not by subgroup).

No interim analyses will be performed and no p-value will be calculated for each subgroup separately. Therefore, no adjustment for multiplicity will be needed.

Secondary and exploratory analyses are purely descriptive even if p-values will be presented, therefore no multiplicity issues are present. No p-value will be provided by subgroup.

Summary of TEAEs will also be presented by relevant subgroups (e.g., by age group [<65 years and ≥ 65 years], sex, race [white, non-white and unknown], and BMI [<30 kg/m² and ≥ 30 kg/m²]).

Likewise, blinding and randomisation is not applicable in this single-arm, open-label trial.

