4.9. Exploratory analyses

The following exploratory endpoints will be analyzed and summarised by visit using FAS for absolute value and change from baseline.

- Anti-CNTN1 and anti-NF155 antibodies titers at EOS visit
- FcγRIIB B cells marker levels at visits V2, V3 and V4
- BAFF and complement components (C3 and C4 antigens, CH50) at visits V2, V3, V4 and EOS visit
- Serum total IgG trough levels before each course

In order to explore the relationship between the biomarkers and clinical response at EOS a univariate logistic regression model will be applied. Each biomarker will be studied separately at each visit. The by visit univariate model will use the biomarker change from baseline (quantitative) as a single exploratory variable, with the clinical response at EOS being the dependent variable.

To explore the relationship of the total IgG trough level and the adjusted INCAT disability score a linear mixed model will be used using the patient as random factor. A scatterplot will show all values and the estimated regression line and its 95% confidence band.

A non-parametric regression method will also be applied (e.g. LOESS, splines or generalised additive models) in order to explore departures from linearity. The result of the estimated regression line will also be shown in a scatterplot together with the 95% confidence band. Similar exploration of the relationship between the biomarkers and other clinical response variables will be conducted as needed using generalized linear mixed models.

A listing of the biomarker data will be produced. In addition, a listing of patients included in the ultrasonography ancillary study will be provided. However, no statistical analysis will be done (see section [4.10.3](#)). The listing will include information on the consent date for the ancillary study and whether data were collected (Yes/No).

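### Exploratory, minor: the IgG-trough/adjusted-INCAT mixed model in SAP 4.9 states no visit term, so a shared time course can look like an IgG effect

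*SAP*

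**What the plan says.** SAP 4.9 gives one sentence to this model: "To explore the relationship of the total IgG trough level and the adjusted INCAT disability score a linear mixed model will be used". The only structure that the sentence names is a random effect for patient. It does not say which variable is the outcome, lists no fixed effects, and does not restrict the data to on-treatment values.

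The IgG variable in the same section is "Serum total IgG trough levels before each course". Course 1 is one of those courses. Protocol 8.2.2 places both the IgG sample and the baseline INCAT under "Before the 1st study drug course (within 24 hours before study drug course"), so the Visit 2 pair precedes any study drug. The SAP 2.6 row "Serum Total IgG trough levels" marks V2, V4 to V10 and V11.

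The display pools the visits too: "A scatterplot will show all values and the estimated regression line and its 95% confidence band". A non-parametric smoother follows, again with no mention of visit. The section then adds: "Similar exploration of the relationship between the biomarkers and other clinical response variables will be conducted as needed using generalized linear mixed models".

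The logistic models in 4.9 differ. They are fitted separately at each visit on change from baseline. Protocol 12.11 leaves the detail of these relationships to the SAP, and the list of changes in SAP 4.10 does not mention this model.

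**The concern.** Visit 2 is an off-treatment value: under the inclusion criteria patients are Ig-naïve or at least 3 months from their last Ig course. Every later trough follows at least one course. Protocol 1.4 expects neurological improvement over the same weeks. A model that pools all visits without a time term attributes that common movement to IgG.

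At stake is the first exploratory objective (Protocol 2.3), which asks whether IgG trough relates to clinical response. A falling line with its 95% band could be read as higher trough, less disability, when it shows only time on treatment.

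**Working it through.** **1. Plan's own figure.** The documents give no figure for this model. The simulations use the planned 38 evaluable patients, which reproduces: exact binomial test, 33.3% against 60%, one-sided 2.5%, n = 38, reject at 19 or more responders, alpha 0.0244, power 92.2% (n = 37 gives 89.2%).

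**2. Paired visits.** V2, V4–V10 and V11 give 9 pairs per patient: one pre-treatment and eight later.

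**3. Direction of IgG.** Protocol 1.3.2 gives a half-life of 33.6 days (PID patients); courses are 21 days apart. In a one-compartment approximation (an assumption) the fraction left is 2^(−21/33.6) = 0.648. In units of a 1 g/kg dose, trough excess is 0 at V2, 2 × 0.648 = 1.30 at V4, (1.30 + 1) × 0.648 = 1.49 at V5, and 1.82 at EOS by the same recursion. Troughs jump after V2 and then drift up.

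**4. Why the slope turns negative.** With IgG and INCAT independent within and between patients, the within-patient slope is roughly

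slope ≈ cov(mean IgG curve, mean INCAT curve) / [var(mean IgG curve) + within-patient IgG variance × 8/9].

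Example, all values assumed: IgG steps up 6 g/L after V2 and stays flat; mean INCAT falls towards −1.2 as 1 − exp(−t/2), t in visits; within-patient IgG SD 1.5.
- Mean fall over the eight later visits: 1.2 × (1 − 1.513/8) = 0.973.
- Covariance: (1/9)(8/9) × 6 × (−0.973) = −0.577.
- Denominator: (1/9)(8/9) × 36 + 2.25 × 8/9 = 3.56 + 2.00 = 5.56.
- Slope: −0.577/5.56 = −0.104 per g/L. The simulated value is −0.098.

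If either mean curve is flat the covariance is zero. A categorical visit term removes both mean curves, so the expected slope is again zero.

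**5. Simulation, no visit term, no patient-level link.** Random intercept, REML, INCAT rounded and clipped to 0–9, 200–400 runs per scenario. Assumed SDs: IgG 2.5 between and 1.5–2.5 within patients; INCAT 1.5 between and 0.7–1.0 within.

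| IgG rise (g/L), INCAT fall | Mean slope | Negative | p < 0.05 |
|---|---|---|---|
| 6, 1.2 | −0.10 to −0.12 | 100% | 100% |
| 6, 0.6 | −0.049 | 100% | 84.5% |
| 4, 0.8 | −0.049 | 99% | 65% |
| 3, 0.6 | −0.016 to −0.041 | 77–94% | 12–43% |
| 2, 0.4 | −0.015 | 75% | 9% |
| 6, 0 | about 0 | 51% | 6% |
| 0, 1.2 | about 0 | 49% | 5.5% |

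With visit added, over the same scenarios: mean slope −0.002 to +0.003, negative in 42–55%, p < 0.05 in 3.5–8.5%.

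**6. Sensitivity to the unknown variances.** Share of trials whose 95% interval excludes zero, no visit term. In the flat-trough column IgG visit noise runs over 1–2.5, INCAT noise over 0.5–1.0, and the SD of patients' INCAT change is 0.5 or 1.5.

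| Rise, fall | Troughs flat after V4 | Troughs rising gradually |
|---|---|---|
| 2, 0.5 | 6–51% | 6–82% |
| 4, 0.5 | 17–84% | 22–99% |
| 4, 1.0 | 40–100% | 45–100% |

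The slope was negative in 69–100% (flat) and 68–100% (gradual). With visit added in the gradual case it was negative in 43–55%, and the interval excluded zero in 4–8%.

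**7. Dropping V2 instead.** With gradually accumulating troughs and no visit term, the slope from V4 onwards was still negative in 54–100% of runs. Excluding V2 is not a substitute for the visit term.

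**The case against.** The strongest reply has four parts.

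- **The SAP is silent, not wrong.** A visit term could still be added at programming. That is so, but Protocol 12.11 sends this detail to the SAP, and the sentence as written, with one line over all values, leads to the pooled fit.
- **The exploratory objective has another, unaffected analysis.** Total IgG is listed under the biomarker study in SAP 2.5.4 and among the endpoints just before the by-visit logistic model, so that model appears to cover it without pooling visits. This stands as the natural reading, though Protocol 2.3 names IgG and biomarkers separately.
- **The time course will be visible.** IgG is summarised by visit and INCAT is plotted over time, and SAP 3.4 says: "Secondary and exploratory analyses are purely descriptive even if p-values will be presented". This limits the harm. It does not make the slope answer the intended question.
- **A visit term changes the question.** All patients follow one schedule, so it also removes any real before/after-treatment association. It does not guarantee nominal error either: over a wider grid of scenarios the visit-adjusted interval excluded zero in 3–21% with no link, because a random intercept alone does not absorb widely differing patient changes. Both points stand. The term removes the bias in direction, not every excess.

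A reader might infer that the model will almost certainly produce a falsely significant IgG effect. The documents do not support that. They give no IgG values and no IgG or INCAT variances, and the tables show how far the result moves with them.

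**Conclusion.** The point holds as a minor, exploratory improvement. Fitted as SAP 4.9 reads, the slope mixes any IgG–disability relation with time on treatment. If both mean curves move, it is negative in about 70–100% of simulated trials without any patient-level link; if either is flat, in about half. The direction needs only the two trends. The chance that the interval excludes zero rests on assumed rises, falls and SDs, and ranges too widely to quote one number.

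A reader might also infer that the responder result or the logistic biomarker models are compromised. They are not: the primary test, secondary endpoints and safety analyses do not use this model, and the logistic models do not pool visits. Nor do the documents show that a visit term was considered and rejected; it is simply not stated.

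**What to change.** In SAP 4.9:

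- State the outcome and the fixed effects, for example adjusted INCAT at a visit on IgG trough at the same visit plus visit as a categorical fixed effect, with a random patient intercept.
- Carry the visit term into any further biomarker mixed models.
- Show the scatterplot and smoother by visit or adjusted for visit. The unadjusted line may stay if labelled as including the time course.
- Optionally, refit on V4 to EOS with the visit term kept.

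The cost is one model term and redrawn plots, from data already collected. The interval will be wider, and the slope will describe same-visit differences in place of the before/after-treatment contrast; the text should say so.

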3.1.4. Treatment

Patients who meet all the eligibility criteria will receive one dose of study drug at 2 g/kg over 2 to 5 days. Three (3) weeks later, they will start to receive 7 doses of study drug at 1 g/kg over 1 to 2 day(s) each, every 3 weeks (+/- 7 days).

Investigators or Study Nurses will call patients 4 days (+/-1 day) after the end of each study treatment course to document potential AEs and TAAEs (see Section [8.2.4](#)).

Duration of the treatment period will be approximately 21 weeks.

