10. ASSESSMENT OF EFFICACY AND SAFETY

10.1. Assessment of Efficacy

10.1.1. Primary Assessment

The INCAT disability score will be assessed by the Investigator at screening, before each study drug course throughout the study and at the end of study assessment. The adjusted INCAT disability score will be deduced from the reported values.

The INCAT disability score measures the disability of both upper and lower limbs, each with a score from 0 (normal) to 5 (maximal disability) [32]. The total score may vary from 0 to 10. The adjusted and original INCAT disability scales are presented in Appendices 20.1.1 and 20.1.2.

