2.1.2. Secondary objectives

The secondary objective of this study is to assess the safety of I10E in patients with CIDP.

The secondary objectives also include the following exploratory objectives:

- To assess a potential relationship between serum total IgG trough levels, biomarkers levels and clinical response - as assessed by neurological scales - in patients with CIDP.
- To assess a potential relationship between ultrasonography (USG) coupled to neurophysiology analysis of nerves and clinical response - as assessed by neurological scales - in patients with CIDP (ancillary study in Italy).

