The CGI-S (*Severity of illness*) assessment by patients and investigators will be presented side by side with descriptive statistics at the visits baseline, week 12 and EOS for the categories *Normal*,

not at all ill / Borderline ill / Mildly ill / Moderately ill / Markedly ill / Severely ill / Among the most extremely ill patients (only for the investigator judgment). A shift table will be provided for the change from baseline at week 12 and EOS.

The CGI-I (*Improvement*) assessment by patients and investigators will be presented side by side with descriptive statistics at the visits week 12 and EOS for the categories *Very much improved / Much improved / Minimally improved / No change / Minimally worse / Much worse / Very much worse*.

The CGI-E (*Efficacy index*) assessment by patients and investigators will be presented with descriptive statistics at the visits week 12 and EOS in a 4×4 cross-table crossing Therapeutic effect categories (*Marked / Moderate / Minimal / Unchanged or Worse*) with Side effect categories (*None / Do not significantly interfere with patient's functioning / Significantly interferes with patient's functioning / Outweighs therapeutic effect*). The sum over the number and % of patients shown the 4×4 cross-table (16 cells) will correspond to the number of patients with valid assessments and 100% respectively. The cross-table will also show a row and column with the Total for each dimension corresponding to the separate description of the Therapeutic effect and the Side effects.

For the endpoints 4) to 8) the one sample Hodges-Lehmann estimator ([Hodges 1963](#) and [Han 2008](#)) and the associated 95% confidence interval will be calculated for all at-visit values, as well as for the change from baseline to 12 weeks and EOS visit for both the overall and patient subgroups. The change from baseline for the endpoints 4) to 8) will be tested using a one sample Wilcoxon signed-rank test, for the overall set of patient only. All statistical tests will be descriptive and will use a two-sided significance level of $\alpha=5\%$.

Statistical tests will not be performed by subgroup.

For all secondary efficacy endpoints, assessments performed after the use of a non-allowed treatment will be censored (not used in the statistical summaries).

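### Exploratory IgG-trough model (SAP 4.9): with patient as the only named random factor, the slope's 95% band and descriptive p-value are too optimistic if both trough and INCAT are serially correlated; state a visit term and a robust or serial error structure.

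*SAP*

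**What the plan says.** SAP 4.9 explores total IgG trough against the adjusted INCAT score as follows: "a linear mixed model will be used using the patient as random factor". The output is graphical: "A scatterplot will show all values and the estimated regression line and its 95% confidence band". A non-parametric regression follows, to look for departures from linearity, and generalised linear mixed models may be used for other biomarkers and responses as needed. SAP 4.9 names no residual covariance, visit or time effect, random slope, degrees of freedom or robust standard error for the mixed model. It sets no threshold for concluding that a relationship exists.

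The analysis serves a stated exploratory aim (SAP 2.1.2): "To assess a potential relationship between serum total IgG trough levels, biomarkers levels and clinical response". SAP 3.4 fixes its status: "Secondary and exploratory analyses are purely descriptive even if p-values will be presented".

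The data are repeated measures. SAP 4.9 lists "Serum total IgG trough levels before each course", and the study plan table (SAP 2.6) adds a trough at the end-of-study visit. INCAT is scored at screening, then "before each study drug course throughout the study and at the end of study assessment" (Protocol 10.1.1). That gives up to nine pairs per patient (Visits 2 and 4 to 11), about three weeks apart with a seven-day window (Protocol 3.1.4).

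**The concern.** A random intercept lets patients differ in level, but it treats a patient's departures from that level as unrelated from one visit to the next. Neither variable is likely to behave so here. With infusions every three weeks, part of a trough deviation carries over to the next trough. Adjusted INCAT is a coarse 0-9 scale, on which a patient who improves by a point may well stay there for several visits.

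When predictor and outcome both persist within patients, nine pairs carry less information about the slope than nine independent pairs would. The model-based standard error does not reflect this. The 95% band around the line would then cover less than 95% in its slope component, and the p-value would overstate the evidence. A trough level unrelated to disability could look linked to it, and the same omission could pass to the follow-on mixed models.

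**Working it through.** **Inputs from the documents**
- 38 evaluable patients, 42 included (SAP 2.3).
- Up to nine pairs per patient, 21 days apart.
- IgG terminal half-life of 33.6 days, observed in primary immune deficiency patients (Protocol 1.3.2).

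**Assumptions**
- Lag-1 correlations: none are given, so a range is shown.
- A two-sided 5% level. SAP 4.6.2 sets this for the secondary endpoints ("All statistical tests will be descriptive and will use a two-sided significance level of" 5%); no level is stated for this model.
- INCAT as the outcome; the SAP does not say which variable is dependent.

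**The plan's own figure.** The plan gives no figure for this model. The patient number does reproduce: with 38 patients and success at 19 or more responders, the exact one-sided error is 0.0244 at 33.3% and power is 0.922 at 60%. With 37 patients power is 0.892.

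**Model as read.** INCAT_ij = a + b·IgG_ij + u_i + e_ij, with e_ij independent. For long series with lag-1 correlations r_x and r_y, the true variance of the slope exceeds the model's by a factor of about (1 + r_x·r_y)/(1 − r_x·r_y). The factor is 1 if either correlation is zero, so both series must persist for any harm to arise. With only nine visits this is a rough guide, so the size was simulated.

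**Simulation under no relationship.** 38 patients, nine visits, the two series generated independently as patient level plus first-order autoregressive deviations; 4,000 trials per setting. The Monte Carlo standard error at 5% is √(0.05 × 0.95/4000) = 0.3 percentage points. Rejection rates at nominal 5%:

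| Lag-1 correlation, both series | Random intercept | Random intercept, integer 0-9 scores | Patient-clustered errors |
|---|---|---|---|
| 0 | 5.4% | 5.0% | 5.3% |
| 0.3 | 7.0% | 7.2% | 5.9% |
| 0.5 | 9.3% | 8.8% | 4.9% |
| 0.7 | 15.7% | 14.9% | 6.5% |
| 0.8 | 17.8% | 16.8% | 6.0% |
| 0.9 | 22.2% | 18.6% | 6.3% |

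Results for 42 patients are nearly the same. Other runs with the same correlations put the rate as high as 11% at 0.5 and as low as 13% near 0.7, hence the ranges quoted. With score correlation 0.7 and trough correlation 0, the rate is 5.2%.

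**In terms of the standard error.** A rejection rate p corresponds to a reported-to-true standard error ratio of z(1 − p/2)/1.96:
- 9.3%: 1.68/1.96 = 0.86, about 14% too small.
- 15.7%: 1.42/1.96 = 0.72, about 28% too small.
- 22.2%: 1.22/1.96 = 0.62, about 38% too small.

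**A partial anchor for the trough.** Carry-over across one interval is 2^(−21/33.6) = 0.65. With trough correlation fixed there (8,000 trials), the rate is about 8% at score correlation 0.3, 11% at 0.5, 14% at 0.7 and 17-18% at 0.9. If 30% of the within-patient variance in both series is uncorrelated noise, these fall to about 6-9%, or 1.2 to 1.8 times nominal.

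**Remedies on the same null.** Patient-clustered errors give 4.7-6.5% across settings. An autoregressive residual added to the random intercept gives 5.2%, 6.2% and 5.0% at correlations 0.5, 0.7 and 0.8 (600 trials each).

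**Shared time trend.** All patients go from no study drug at Visit 2 to repeated dosing, so trough may rise and INCAT fall together whether or not they are related. With an assumed common shift after the first course of 1.5 within-patient SD in one series and 1.0 in the other:

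| Correlation, both | No visit, model errors | No visit, clustered | Visit, model errors | Visit, clustered |
|---|---|---|---|---|
| 0 | 65% | 65% | 5.5% | 5.6% |
| 0.5 | 79% | 69% | 9.9% | 5.4% |
| 0.7 | 88% | 78% | 16.0% | 6.0% |

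Neither change is sufficient by itself when both features are present; the two together are.

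**The case against.** The strongest reply is that this is an exploratory plot with no decision attached. SAP 3.4 calls such analyses descriptive even where p-values appear, and SAP 4.9 asks only for a line and a band. That stands, and it sets the weight of the point. It does not fully answer it: descriptive status excuses the lack of multiplicity control, but a band labelled 95% should still have about that coverage.

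It is also fair that the SAP does not rule out a residual correlation. It is silent, so this is under-specification rather than a stated assumption of independence. Protocol 12.11 leaves the detail of these analyses to the SAP, so SAP 4.9 is where it belongs.

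Three stronger readings are tempting, and the documents do not support them:
- A reader might infer that the model declares a relationship two to four times too often. No correlation is given, so the factor runs from none to about four (22.2/5 = 4.4 at 0.9 in both series). With no threshold set, nothing is declared.
- A reader might take the half-life as fixing the trough correlation. It comes from another disease, and INCAT has no counterpart.
- A reader might think this the only analysis of trough against INCAT. The non-parametric fit in SAP 4.9 addresses the same relationship.

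**Conclusion.** The point holds in a limited form. As plainly read, the model gives a slope standard error that is too small when both trough and INCAT are serially correlated within patients. At an assumed lag-1 correlation of 0.5 in both, the nominal 5% rate is about 9-11%; at 0.7 to 0.9 it is about 13-22%. Up to 0.3 it is 5-7%, with 30% uncorrelated noise about 6-9%, and if either series is uncorrelated there is no inflation. These sizes rest on assumed autoregressive correlations, on reading the SAP's silence as independent residuals, and on a 5% level borrowed from the secondary endpoints. The consequence is confined to an exploratory band and p-value. The primary test, its error rate and the sample size are unaffected. It is worth fixing because the change is small, not because a main conclusion is at risk.

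**What to change.** In SAP 4.9:
- Keep patient as the random factor and add visit as a categorical fixed effect.
- Take the confidence interval, band and p-value for the IgG slope from patient-clustered (empirical sandwich) standard errors with between-patient degrees of freedom. In SAS this is the EMPIRICAL option of PROC MIXED. Alternatively, specify a spatial-power residual correlation by actual study day, which also allows for the visit windows.
- Label the p-value descriptive, in line with SAP 3.4.
- Apply the same rule to any follow-on generalised linear mixed models.

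The visit term and the error structure should go in together, because clustered errors alone do not remove a shared time trend.

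Cost: a sentence or two in the SAP, a model term and a software option; no new data. The price is a somewhat wider band and less nominal significance in an exploratory analysis.
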